#### DMID/NIAID/NIH

#### CONFIDENTIAL

sampling time. Ten additional enrolled subjects will act as alternates to obtain 30 evaluable subjects.

Each subject will complete Screening, Baseline, Treatment and Follow-up Phases. The Screening Phase will be conducted on an outpatient basis within 30 days of the Baseline Phase, which will consist of admission to DEPRU on the day before the first dose (Day -1) for pre-dosing assessments. The Treatment Phase will start on the day of first dose (Day 1) and end at the time of discharge from DEPRU. Three IV doses of ZTI-01 will be administered every 8 hours (hours 0, 8, and 16 during the Treatment Phase). Blood samples for PK measurements will be collected before each dose, up to 8 hours after the start of the first IV infusion of ZTI-01, and up to 12 hours after the start of the third IV infusion (Tables 2 and 3). One bronchoscopy with BAL will be completed on each subject at the timepoint to which that subject was randomized. Key electrolytes will be remeasured prior to each subject's bronchoscopy in order to minimize risk of arrhythmia. Subjects will be discharged following the final 12-hour blood sampling time point (if safety parameters are acceptable to the Investigator). Safety assessments will be conducted during the entire 24-hour Treatment Phase. The Follow-Up Phase consists of a telephone interview on Day 3 for symptom-driven safety assessments.

Estimated Time to Complete	
Enrollment:	

Approximately 12 weeks

DMID/NIAID/NIH

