#### DMID/NIAID/NIH

#### CONFIDENTIAL

will be measured prior to subjects undergoing the stress of bronchoscopy. Subjects with grade II or higher abnormalities in these electrolytes will not undergo bronchoscopy.

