#### DMID/NIAID/NIH

#### CONFIDENTIAL

- Obtain PK blood samples at 15 timepoints: before (within 10 minutes) the first, second, and third doses of study drug, at 30 minutes (during infusion), 1 hour (within 5 minutes after the end of infusion), 1 hour 15 minutes, 2, and 5 hours from the start time of the first infusion of ZTI-01, and at 30 minutes (during infusion), 1 hour (within 5 minutes after the end of infusion), 1 hour 15 minutes, 2, 5, 8, and 12 hours from the start time of the third (last) infusion of ZTI-01
- Measurement of sodium, potassium, magnesium, calcium, and phosphorus approximately 2 hours prior to the assigned bronchoscopy timepoint
- A standardized bronchoscopy with BAL sampling will be performed at single timepoint based on each subject's schedule assignment at either 30 minutes, 1 hour 15 minutes, 2, 5, or 8 hours after the start time of the third (last) infusion of ZTI-01
- Collect a blood sample to measure serum urea concentration just before or during bronchoscopy

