#### 8.2.2. Bronchoscopy and Bronchoalveolar Lavage (BAL)

Each subject will be assigned to one bronchoscopy sampling timepoint. The bronchoscopy sampling times will be at 30 minutes, 1 hour 15 minutes, 2, 5, and 8 hours from the start time of the third (last) infusion of ZTI-01. A total of 6 subjects will be assigned to each of the five BAL sampling times.

Sodium, potassium, magnesium, calcium, and phosphorus will be measured approximately 2 hours prior to each subject's bronchoscopy timepoint. Subjects with grade 2 or higher abnormalities (Appendix B) in these electrolytes will not receive any further study product and will not undergo bronchoscopy.

Bronchoscopy will be performed in a standardized fashion according to the MOP. Topical lidocaine will be applied to the upper airways to prepare subjects for bronchoscopy. If needed, 1.0% percent lidocaine

CONFIDENTIAL

DMID Protocol 16-0058	Version 9.0
IV Fosfomycin PK Study	27 August 2020

will be used in the lower airway. A fiberoptic bronchoscope will be inserted into the right middle lobe. Four 50-mL aliquots of sterile normal saline will be instilled into the right middle lobe and each specimen will be immediately aspirated and placed on ice. BAL samples for PK measures will be obtained  $\pm 15$  minutes from the subject's assigned sampling time. The start and stop times of BAL will be recorded on the eCRF.

Subjects will be continuously monitored during bronchoscopy. Blood pressure, heart rate, respiratory rate, and peripheral oxygen saturation will be recorded before and at the end of bronchoscopy. Subjects will undergo cardiac monitoring during bronchoscopy.

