# 9.5. Halting Rules

If any of the halting rules, as outlined below, is met, further enrollment and dosing will be withheld until the SMC reviews the safety data and provides its recommendations.

- Two subjects experience any related Grade 3 systemic AE
- Two subjects experience the same related Grade 3 laboratory AE (per Medical Dictionary for Regulatory Activities High Level Group Term)
- One subject experiences a related SAE

A decision to reinitiate the trial and proceed with study drug administration will be made by DMID based on the recommendation of the SMC.

If the following individual halting rule is met, the individual will not undergo further dosing or study procedures.

• Subject experiences a grade 2 or higher abnormality in sodium, potassium, magnesium, calcium, or phosphorus, when checked approximately 2 hours prior to the bronchoscopy timepoint

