#### DMID/NIAID/NIH

CONFIDENTIAL

e Alcohol history within past 6 months, lifetime tobacco history

- f ECGs will be performed in the supine or semi-recumbent position (after rest for at least 10 min) at 3 timepoints: at Screening, Day 1 (before first dose of Study Drug), and within 1-2 hours of the last dose (3rd dose) of study drug. In case of premature discontinuation of study drug, ECG is to be performed before discharge.
- g At Screening, and before discharge (Day 2), obtain hematology labs (white blood cell count, hemoglobin, hematocrit, and platelet count, neutrophils, lymphocytes, monocytes, eosinophils, basophils); coagulation tests (aPTT and PT), chemistry labs (albumin, glucose, blood urea nitrogen (BUN), potassium, magnesium, calcium, sodium, phosphorus, total protein, creatinine, triglycerides, total cholesterol, CPK, phosphorus, AST, ALT, total bilirubin, direct bilirubin, ALP, LDH), and urinalysis (leukocyte esterase, blood, glucose, protein, pH, and specific gravity via dipstick with addition of urine microscopy if dipstick abnormal). At Baseline (Day -1 to Day 1) obtain albumin, glucose, BUN, potassium, magnesium, calcium, sodium, phosphorus, total protein, creatinine, CPK, AST, ALT, total bilirubin, and ALP. Approximately two hours prior to bronchoscopy (Day 2) obtain sodium, potassium, magnesium, calcium, and phosphorus.
- h Serum pregnancy test for women of childbearing potential at screening, and urine pregnancy test for women of childbearing potential at Baseline (Day -1 to Day 1)
- i Alcohol Breathalyzer test, Urine cotinine, and Urine drug screen at Screening and Baseline (Day -1 to Day 1/admission to DEPRU). Cotinine will be reported qualitatively as positive/negative. Urine drug screen will consist of: barbiturates, benzodiazepines, THC, cocaine, opiates, and amphetamine/methamphetamine.
- j. Test for SARS-CoV-2 (COVID-19) at Screening or Baseline (Day -1 to Day 1) within 72 hours of admission
- k Subjects will receive a total of three doses of ZTI-01 (fosfomycin disodium) 6g, administered every 8 hours, as 1-hour intravenous infusion (+10 minute window)
-  Blood sample to determine plasma urea concentration will be obtained just before or during the scheduled bronchoscopy

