10.2. Dosing and Pharmacokinetic Sampling Summary

Subject infusion start and end times (including interruptions) for all infusions received will be presented for each subject (Listing 7). If infusion of the drug is interrupted, the start and end times of the interruption will be recorded. Regardless of the amount of study product received, all scheduled blood draws will be attempted to be collected within a window based on the start of the administration. Special cases that potentially affect the analysis will be discussed in the final report. Actual infusion duration will be used for NCA analysis. If actual infusion duration time is missing, a duration of 1 h will be imputed.

Fosfomycin concentrations in plasma will be listed by subject and infusion dose number, with BQL and out of sample time window samples indicated (Listing 25). Fosfomycin concentrations in BAL and cell pellet samples concentrations will be listed by subject with out of sample time window samples indicated (Listing 27). The listings will also indicate the nominal and actual time associated with the sample.

Nominal time is defined as the time in hours since the start of infusion of either Dose 1 or Dose 3 as shown below:

Dose 1

- Timing of PK sample = "Pre-Dose for Dose 1", Nominal Time = 0 h
- Timing of PK sample = "30 minutes after starting the first dose", Nominal Time = 0.5 h
- Timing of PK sample = "1 hour after starting the first dose", Nominal Time = 1 h
- Timing of PK sample = "1 hour 15 minutes after starting the first dose", Nominal Time = 1.25 h
- Timing of PK sample = "2 hours after starting the first dose", Nominal Time = 2 h
- Timing of PK sample = "5 hours after starting the first dose", Nominal Time = 5 h
- Timing of PK sample = "Pre-Dose for Dose 2", Nominal Time = 8 h

Dose 3

- Timing of PK sample = "Pre-Dose for Dose 3", Nominal Time = 0 h
- Timing of PK sample = "30 minutes after starting the third dose", Nominal Time = 0.5 h

- Timing of PK sample = "1 hour after starting the third dose", Nominal Time = 1 h
- Timing of PK sample = "1 hour 15 minutes after starting the third dose", Nominal Time = 1.25 h
- Timing of PK sample = "2 hours after starting the third dose", Nominal Time = 2 h
- Timing of PK sample = "5 hours after starting the third dose", Nominal Time = 5 h
- Timing of PK sample = "8 hours after starting the third dose", Nominal Time = 8 h
- Timing of PK sample = "12 hours after starting the third dose", Nominal Time = 12 h

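### In the 2 h arm, and in the 1.25 h arm unless laboratory turnaround is 45 min or less, the electrolyte check that must stop further study drug comes too late to keep Dose 3 from starting

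*Protocol*

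**What the plan says.** **Timing of the check.** Protocol 7.3 schedules it by bronchoscopy: "Measurement of sodium, potassium, magnesium, calcium, and phosphorus approximately 2 hours prior to the assigned bronchoscopy timepoint". Sections 8.2.1 and 8.2.2, Appendix A footnote g ("Approximately two hours prior to bronchoscopy (Day 2) obtain sodium, potassium, magnesium, calcium, and phosphorus") and SAP 4.5.1 and 9.6 use the same anchor. The Protocol Summary gives the purpose: "Key electrolytes will be remeasured prior to each subject's bronchoscopy in order to minimize risk of arrhythmia".

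**Consequence of a Grade 2 or higher value.** The operative sections attach a dosing stop to this check.
- Section 8.2.2: subjects who reach Grade 2 or higher on any of these "electrolytes will not receive any further study product and will not undergo bronchoscopy".
- Section 9.5, individual halting rule: "the individual will not undergo further dosing or study procedures", triggered by such a value "when checked approximately 2 hours prior to the bronchoscopy timepoint".
- Section 2.3.1 mentions only the procedure: "Subjects with grade II or higher abnormalities in these electrolytes will not undergo bronchoscopy".

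**What is absent.** Neither document gives a laboratory turnaround time or a window around the 2 h, and neither tells staff to hold Dose 3 until the result is seen.

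**The concern.** After Baseline, this draw is the only scheduled electrolyte measurement that could lead to Dose 3 being withheld; the next one is at discharge (8.2.1). By then a subject has received two doses, 12 g of fosfomycin with 2 x 1980 = 3960 mg of sodium (6.2), and Section 2.3.1 links the sodium load to hypokalemia. A rule that withholds further drug can protect a subject only if its result arrives while drug remains to be withheld. Because the draw follows the bronchoscopy time, whether that happens depends on the arm. At stake is part or all of one 6 g infusion given to a subject who already has an abnormality that the protocol treats as a reason to stop.

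**Working it through.** **Inputs from the documents.** BAL at 0.5, 1.25, 2, 5 and 8 h after the start of Dose 3, with 6 subjects at each time (Table 2; 8.2.2). Electrolyte draw about 2 h before BAL (7.3). Dose 3 is the last dose, 6 g over a nominal 60 min (6.2).

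**Plan's own figure.** 30 subjects / 5 sampling times = 6 per arm, which agrees with Table 2.

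**Step 1. Draw relative to Dose 3 start = BAL time - 120 min.**

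| Arm | n | Draw | Position |
|---|---|---|---|
| 0.5 h | 6 | 30 - 120 = -90 min | 90 min before Dose 3 |
| 1.25 h | 6 | 75 - 120 = -45 min | 45 min before |
| 2 h | 6 | 120 - 120 = 0 min | at the start |
| 5 h | 6 | 300 - 120 = +180 min | 120 min after nominal end |
| 8 h | 6 | 480 - 120 = +360 min | 300 min after nominal end |

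**Step 2. Amount of Dose 3 already given when the result arrives.** The infusion rate is 6 g / 60 min = 0.1 g/min. For turnaround T, amount = 0.1 x min(60, max(0, draw + T)). T is an assumption. The bronchoscopy gate works only if T is at most 120 min, so that is the range shown.

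| T | 0.5 h arm | 1.25 h arm | 2 h arm |
|---|---|---|---|
| 30 min | 0 g | 0 g | 3 g |
| 60 min | 0 g | 1.5 g | 6 g |
| 90 min | 0 g | 4.5 g | 6 g |
| 120 min | 3 g | 6 g | 6 g |

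At the scheduled time the 2 h arm misses the start of Dose 3 for any positive T. The 1.25 h arm misses it only when T exceeds 45 min.

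**Step 3. How often it might matter.** The documents give no Grade 2 rate, so p = 1%, 5% and 10% are assumptions only. The chance that at least one subject starts Dose 3 with an unseen Grade 2 value is 1 - (1 - p)^n.
- T up to 45 min (2 h arm only, n = 6): 5.9%, 26.5%, 46.9%.
- T above 45 and up to 90 min (both arms, n = 12): 11.4%, 46.0%, 71.8%.

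**Step 4. Effect of moving the draw to -90 min in both arms.** For T up to 90 min, no Dose 3 has been given when the result arrives. The draw-to-bronchoscopy gap becomes 75 + 90 = 165 min (2.75 h) and 120 + 90 = 210 min (3.5 h).

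**The case against.** The best defence is that the check was designed as an arrhythmia gate before bronchoscopy, as the Protocol Summary and 2.3.1 say, and that it does this job with a 2 h lead in every arm. That stands. It does not remove the point, because 8.2.2 and 9.5 expressly add a dosing stop to the same check.

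A reader might infer that starting Dose 3 before the result is known breaks the rule. It does not: the stop looks forward, and nothing is ordered until a Grade 2 value has been found. A running infusion could then be interrupted.

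A reader might also count all 12 subjects in the two arms as certain to be affected, or add the 12 in the 5 h and 8 h arms. Only the 2 h arm is affected at every turnaround. In the two late arms no dose remains at the check, so the dosing stop simply has no effect. Those subjects do start Dose 3 without a post-baseline electrolyte value, but no section orders a check before Dose 3. Moving their draw to -90 min would place it 5 + 1.5 = 6.5 h and 8 + 1.5 = 9.5 h before bronchoscopy and lose any effect of Dose 3 on the gate value. They would need an extra draw, which is not proposed. In the 1.25 h and 2 h arms the current draw already comes before any effect of Dose 3, so moving it loses nothing of that kind.

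The timing is stated as approximate, and site procedures may help. A draw taken 15 min early (an assumed slack) would give leads of 60 and 15 min, but that is not an instruction to review before dosing. The investigator may withdraw anyone from study drug (5.3.2), but cannot act on a result not yet available.

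The Grade 2 rate is probably low. Footnote 12 to exclusion criterion 25 bars even Grade 1 electrolyte values at entry, and abnormal laboratory findings in the earlier single-dose Phase 1 study were described as mild (2.1). That evidence is indirect for three doses, but it gives no support for the upper end of the assumed range.

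The differing scope of the stop is a matter of wording. Section 2.3.1 is a risk narrative and contradicts neither operative section. SAP 10.2 ("Regardless of the amount of study product received, all scheduled blood draws will be attempted to be collected") is a general rule on incomplete dosing and does not define this stop. Safety follow-up after a stop is largely protected by 5.3.2, 7.6, 8.1 and 9.4. A stopped subject has no BAL, is not evaluable and is replaced (5.3.4), with samples discarded (5.3.3), so no PK estimate changes.

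**Conclusion.** The point holds in a limited form and is minor. In the 2 h arm (6 of 30) the check as scheduled cannot keep Dose 3 from starting. In the 1.25 h arm (6 of 30) it can do so only if turnaround is 45 min or less. The consequence is up to 6 g of study drug in a subject with an unseen Grade 2 value. How often that would occur cannot be estimated from the documents, and the percentages above are only as good as their assumed rates. The amounts also assume a 60 min infusion and a draw exactly 2 h before bronchoscopy. The documents do not support reading this as a failure of the bronchoscopy gate, a breach by the site, or a bias in the PK results.

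**What to change.** In the 1.25 h and 2 h arms, take the planned electrolyte draw about 90 min before the start of Dose 3, as the 0.5 h arm already does, and start Dose 3 only after the result has been reviewed. The 90 min should be checked against the site's turnaround; if that can exceed 90 min, all three early arms need an earlier draw. Leave the 5 h and 8 h arms as they are. Conform Protocol 7.3, 8.2.1, 8.2.2, the trigger in 9.5 and Appendix A footnote g, together with SAP 4.5.1, SAP 9.6, SAP Table 1 footnote g and the row labels in SAP Tables 20 and 21.

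Cost: wording, and a new time for one 4.5 mL draw in 12 of 30 subjects, with total blood unchanged at 122.4 mL. The downside is an older gate value, 2.75 h and 3.5 h before bronchoscopy instead of 2 h, although no drug is infused between the old and new draw times. If the site also wants the 2 h value, a second draw in these two arms brings the total to 122.4 + 4.5 = 126.9 mL. A stopped subject would be replaced in any case, so sparing the dose costs no PK data.

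While amending, align 9.5 with 8.2.2: no bronchoscopy and no remaining study drug, while safety, exit and Day 3 assessments continue. This is a wording tidy-up only.

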# 9.6. Safety Oversight

The safety oversight for the trial will be conducted under the direction of DMID.

#### DMID/NIAID/NIH

CONFIDENTIAL

#### 9.6.1. Independent Safety Monitor (ISM)

An ISM will oversee the safety of subjects and provide independent evaluation of all SAEs and related Grade 3 AEs. The ISM will communicate with the Site Investigators to discuss subject-related issues and resolve queries generated by the ISM, DMID Medical Monitor, and SMC, as applicable.

#### 9.6.2. Safety Monitoring Committee (SMC)

An SMC will be appointed to monitor subject safety. The SMC will consist of independent evaluators who will have no relationship with the conduct of the trial. The SMC will operate under the rules of a DMID-approved charter that will be written at the organizational meeting of the SMC. In the charter, meeting frequency and each data element that the SMC will assess will be clearly defined.

The SMC will review safety data for increased rate of occurrence of serious suspected AEs. If halting rules are met, more frequent meetings may be held. Ad hoc meetings may also be held to address any safety issues that may arise.

If the trial is halted, the SMC will be consulted to review the data and provide a recommendation related to the continued dosing of the subjects.

The SMC will advise DMID of its recommendations. At the end of study enrollment, the SMC will review clinical safety and PK data, and provide recommendations regarding further safety assessments in studies with ZTI-01. Since the study is an open-label trial, a statistician may provide independent analyses to the SMC as needed.

# **10. CLINICAL MONITORING**

Site monitoring of the trial will be conducted to ensure the safety and conduct of the trial complies with 21 CFR 11, 21 CFR 50, 21 CFR 54, 21 CFR 56, 45 CFR 46, 21 CFR 312 GCP and ICH Guidelines, and DMID guidelines, as appropriate.

# 10.1. Site Monitoring Plan

Site monitoring is conducted to ensure that the human subjects' protections, study and laboratory procedures, study intervention administration, and data collection processes are of high quality and meet Sponsor, ICH/GCP guidelines, and applicable regulations, and that the trial is conducted in accordance with the protocol, protocol-specific MOP, and applicable Sponsor SOPs. DMID, the Sponsor, or its designee will conduct site-monitoring visits as detailed in the clinical monitoring plan.

Site visits will be made at standard intervals as defined by DMID and may be made more frequently as directed by DMID. Monitoring visits will include, but are not limited to, review of regulatory files, accountability records, eCRFs, ICFs, medical and laboratory reports, and protocol and GCP compliance. Site monitors will have access to DEPRU, study personnel, and all study documentation according to the DMID-approved site monitoring plan. Study monitors will meet with the Site PI to discuss any problems and actions to be taken, and will document site visit findings and discussions.

# **11. STATISTICAL CONSIDERATIONS**

## 11.1. Study Hypotheses

The objectives of the study are to assess safety and pharmacokinetics for a multiple dose regimen of IVinfused ZTI-01. The study is not designed to test any formal hypotheses, but will provide exposure information on the IV formulation of ZTI-01. These exposure data should act as a bridge between the new IV formulation and the approved oral reference drug.

These data could permit the application of previously submitted information (e.g. safety, pharmacology, toxicology, genotoxicity, carcinogenicity) in support of the new IV formulation.

This study will also provide adequate information to confirm the safety and PK of ZTI-01 and further evaluate its use in the intended patient population.

# **11.2.** Sample Size Considerations

Since statistical analyses are not intended to serve as a basis of definitive conclusions, statistical power considerations for determination of sample size were not performed. The sample size for this study was selected as adequate for determining the safety and PK of ZTI-01. The sample size is based on clinical experience and judgment relative to study design and objectives. The study is designed to enroll 40 healthy male and female adult subjects, aged 18 to 45 years, to have 30 evaluable subjects complete the trial. This will result in 30 plasma and BAL concentration-time profiles available for PK profiling. Table 8 displays probabilities of detecting at least one safety event for a range of true event rates using the specified sample size of 30 subjects. Administration of ZTI-01 to any alternate subjects may result in a sample size higher than 30 for safety analyses. In this case, the probability of observing safety events will be higher than displayed in Table 8.

27 August 2020

True Event Rate	Probability of observing 1 or more events
0.1%	3%
0.5%	14%
1%	26%
2%	45%
5%	79%
7%	89%
10%	96%
15%	99%

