### Table 2: Bronchoscopy with BAL sampling times

	BAL sampling times after start of third IV infusion of ZTI-01*				
	30 minutes	1 hour 15 minutes	2 hours	5 hours	8 hours
No. subjects (n=30 completed)	6	6	6	6	6

\*Each subject will complete a single standardized bronchoscopy with BAL randomized to one of the five sampling times shown.

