# 5.3. Treatment Assignment Procedures

#### 5.3.1. Randomization Procedures

Subjects will be randomized to a single standardized bronchoscopy with BAL sampling timepoint upon study enrollment using an assignment schedule as follows: 30 subjects will be randomized 1:1:1:1:1 to each of the five BAL sampling timepoints (30 minutes, 75 minutes, 2 hours, 5 hours, or 8 hours after the start of the third IV infusion of ZTI-01). Up to ten (10) subjects will be enrolled as alternates. Alternates will arrive at DEPRU on Day -1 to Day 1 and will adopt the planned BAL sampling timepoint of any other enrolled subject who fails to present for check-in or who fails to meet inclusion/exclusion criteria on Day -1 to Day 1. If all scheduled subjects present for check-in and meet Day -1 to Day 1 inclusion/exclusion criteria, then alternates will not undergo any further study procedures at that time. In that case, alternates may be assigned to a new bronchoscopy time on a future date, alternate status for a future date, or as replacement subjects (see Section 5.3.4).

Subjects will be enrolled online using the enrollment module of AdvantageEDCSM software. The randomization code will be prepared by DCC statisticians and included in the enrollment module for this study. AdvantageEDCSM will assign each subject to a sampling timepoint after the demographic and eligibility data have been entered.

Instructions for use of the enrollment module are included in the AdvantageEDCSM User's Guide. Manual back-up procedures and instructions are provided for use in case the site temporarily loses Internet access or the online enrollment system is unavailable.

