Notes: times are related	Jotes: times are relative to time of start of infusion of Dose 3. N = Number of data points used to compute the summary statistics.											

Table 42:Summary Statistics for AM Fosfomycin Concentration (µg/mL) and AM to Plasma
Concentration Ratio by BAL Sampling Timepoint

	AM Fosfo	mycin Con	centration (µg/ı Timepoint	mL) at BAL	Sampling	Concentration Ratio AM to Plasma at BAL Sampling Timepoint						
Statistic	0.5 h	1.25 h	2 h	5 h	8 h	0.5 h	1.25 h	2 h	5 h	8 h		
Ν	х	х	Х	х	х	х	х	Х	х	х		
Mean	х	х	Х	х	х	х	х	Х	х	х		
SD	х	х	Х	х	х	х	х	Х	х	х		
Min	х	х	х	х	х	x	х	Х	х	х		
Median	х	х	х	х	х	x	х	Х	х	х		
Max	х	х	х	х	х	x	х	Х	х	х		
CV%	х	х	х	х	х	x	х	Х	х	х		
GM	х	х	х	х	х	x	х	Х	х	х		
GSD	х	х	Х	х	х	x	х	Х	х	Х		
Notes: times are	e relative to tim	e of start of	infusion of Dos	e 3. N = Nu	mber of data p	oints used	to compute the	summary statis	stics.			

Table 43:Noncompartmental Analysis Population Average AUC0-8 of Fosfomycin in Plasma, ELF,
and AM and Percent Penetration

	Ν	AUC ₍₀₋₈₎ a (h*µg/mL)	Plasma Percent Penetration
Plasma	х	Х	NA
ELF	х	Х	Х
AM	х	Х	Х
Note: N = number of data points used to compute used to derive AUC ₍₀₋₈₎ ^a AUC ₍₀₋₈₎ following Dose 3			

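### Protocol 11.2 counts 30 BAL concentration-time profiles where the design gives 30 single BAL samples, and SAP Table 43 reports the composite penetration estimate without a confidence interval

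*Protocol*

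**What the plan says.** Protocol 11.2 plans 40 enrolments "to have 30 evaluable subjects complete the trial" and continues: "This will result in 30 plasma and BAL concentration-time profiles available for PK profiling".

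The design sections describe the lung sampling differently. The footnote to Protocol Table 2 reads "Each subject will complete a single standardized bronchoscopy with BAL randomized to one of the five sampling times shown". Protocol 8.2.2 says "Each subject will be assigned to one bronchoscopy sampling timepoint" and "A total of 6 subjects will be assigned to each of the five BAL sampling times". Protocol 5.3.1 allocates equally over the five times. Blood is sampled intensively in everyone; Protocol 7.3 has "Obtain PK blood samples at 15 timepoints".

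Protocol 11.3 takes the median concentration at each BAL time, forms one population-average AUC0-8 for each of plasma, ELF and AM, and defines percent penetration as the lung-to-plasma AUC ratio. SAP 10.3.2 starts the same way but then divides by the geometric mean plasma AUC0-8. The result goes into SAP Table 43, "Noncompartmental Analysis Population Average AUC0-8 of Fosfomycin in Plasma, ELF" and AM, whose columns are N, AUC0-8 and percent penetration.

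**The concern.** One BAL sample cannot form a concentration-time profile, so the BAL half of the sentence in 11.2 describes data that the trial will not have. It is the only quantitative statement about PK yield in the sample-size section.

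The same feature of the design affects the result. Each lung matrix yields a single composite AUC, so the summary statistics that SAP 10.3.2 lists for PK measures (SD, CV%, geometric SD and so on) cannot be computed for the penetration ratio. Unless an interval is built on purpose, the ratio appears as a bare percentage. Protocol 2.2 names lung concentration relative to plasma as the first thing the trial should establish. A reader who has seen 30 BAL profiles promised and then one percentage reported is likely to overrate how well it is known.

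**Working it through.** **Inputs from the documents.** 30 evaluable subjects (Protocol 11.2); five BAL times, 0.5, 1.25, 2, 5 and 8 h after the start of the third infusion, six subjects each, one BAL per subject (Protocol Table 2, 5.3.1, 8.2.2); 15 plasma samples per subject (Protocol 7.3). No between-subject CV for ELF, AM or plasma is given.

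**Step 1: count the data.**
- Subjects: 5 × 6 = 30. This reproduces the stated number.
- Plasma: 3 pre-dose + 5 after dose 1 + 7 after dose 3 = 15 samples; 30 × 15 = 450 samples, 30 individual profiles. This agrees with 11.2.
- BAL: 30 × 1 = 30 samples, no individual profiles, and one five-point composite each for ELF and AM. This does not agree with 11.2.

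The numbers in Protocol Table 8 are correct: 1 − (1 − p)^30 gives, for example, 78.5% at p = 5% and 95.8% at p = 10%, and all eight rows match after rounding. The fault in 11.2 is confined to the one sentence.

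**Step 2: what precision is planned for penetration.**
- SAP Table 43: none.
- SAP Tables 41–42: descriptive statistics of the concentrations and ratios at each BAL time, not of the AUC ratio.
- SAP 10.5: median and 95% prediction interval from an exploratory population model, being the 2.5th to 97.5th percentiles of simulated individual ratios with between-subject and without residual variability. It answers how much subjects differ, not how well the Table 43 ratio is estimated.

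**Step 3: one time point alone.** With n = 6, the range from minimum to maximum covers the median with probability 1 − 2(0.5^6) = 0.969. The 2nd to 5th ordered values cover it with probability 1 − 2 × 7 × 0.5^6 = 0.781. A distribution-free 95% interval is therefore the full range.

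**Step 4: the composite.** I simulated trials of 6 × 5 subjects with log-normal variation. Assumptions: plasma log-SD 0.2; ELF/plasma ratio log-SD σ = √ln(1 + CV²); one-compartment shape after a third 1-hour infusion with half-life 2 to 4 h; time-0 value taken as known. The estimator is the AUC0-8 from the five medians (linear up, log down), ELF over plasma.

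| Assumed CV of ratio | σ | 95% sampling range, estimate/truth | A true 50% is reported as |
|---|---|---|---|
| 30% | 0.294 | about 0.87–1.16 | 44–58% |
| 40% | 0.385 | about 0.85–1.22 | 42–61% |
| 50% | 0.472 | about 0.82–1.28 | 41–64% |

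Half-life hardly matters. Nor does the denominator: at 40% CV the lower limit is 0.844 with the median-based plasma AUC (50 × 0.844 = 42.2) and 0.848 with the geometric mean. If the ratio is more variable, as it might be for AM, the range widens. At 80% CV, with plasma treated as known, it is about 0.76–1.45.

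**Step 5: how much the wrong count flatters precision.** With plasma known and 30 real lung profiles, a geometric mean AUC would have a range of exp(±1.96σ/√30): 0.90–1.11 at 30% CV and 0.84–1.18 at 50%. The composite gives 0.88–1.15 and 0.82–1.27. The difference is moderate.

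**The case against.** The case on the other side is substantial, and four parts of it stand.

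- **The sentence is not the basis of the sample size.** A reader might infer that 30 BAL profiles justify calling the sample adequate. Protocol 11.2 instead rests that on experience and clinical judgement, and the profiles sentence only states a consequence. SAP Section 5 keeps the basis and omits the sentence. No estimator depends on it.
- **The plan is not without any interval.** A reader might infer that nothing about spread is reported. SAP 10.5 plans a prediction interval. Tables 41–42 print the minimum and maximum of the ratio at each BAL time, which by step 3 is already a 96.9% interval for that median with six subjects. Figure 50 and Listing 27 show the individual values.
- **Penetration does not rest on six subjects.** Six is right for each ELF or AM median, but the AUC pools all 30 BAL samples. The geometric mean plasma denominator can use all 30 plasma profiles.
- **There is no target to miss.** The documents set no penetration threshold and test no hypothesis, so neither a power calculation nor a comparison with a target is lacking.

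It can also be said that a confidence interval is optional in a descriptive Phase 1 trial. That is correct as far as it goes. The same SAP, however, gives 95% intervals for adverse-event percentages (9.3.1) and for the shift in Tmax (10.3.1). A question ranked first in Protocol 2.2 merits no less.

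**Conclusion.** The point holds in two parts. First, the BAL half of the sentence in Protocol 11.2 is wrong: the yield is 30 plasma profiles and 30 single BAL concentrations, giving one composite profile for each lung matrix. This follows from the documents alone. Second, the main noncompartmental penetration estimate has no confidence interval, and nothing else in the SAP supplies one for it. Adding it is an improvement rather than the repair of a contradiction.

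The size rests on assumed CVs. For 30% to 50%, the estimate would fall within about 13% to 18% below and 16% to 28% above the truth in 95% of trials. Error in the urea dilution measurement is not added separately. The documents do not support reading this as an invalid estimate or an inadequate sample size, and the safety analysis is untouched. They do support saying that the uncertainty is large enough to be shown beside the percentage.

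**What to change.** 1. **Protocol 11.2.** Replace the sentence by: 30 plasma profiles and 30 single BAL concentrations (6 per time), giving one composite profile each for ELF and AM.
2. **SAP 10.3.2.** Settle the denominator: the plasma AUC0-8 built from medians at the BAL times, as in Protocol 11.3, or the geometric mean of the subjects' plasma AUC0-8. The interval cannot be programmed until one is named.
3. **SAP Table 43.** Add a 95% bootstrap interval for the ELF and AM ratios, using the chosen estimator. Resample subjects within BAL time and keep each subject's plasma and BAL values together. Add a note that the interval is approximate with six subjects per stratum. In a check of 400 simulated trials at each of log-SD 0.4 and 0.5, percentile intervals of this kind covered the truth about 96% of the time, so the method is workable under those assumptions.

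The cost is a wording change in each document and one extra program. The downside is that the stated precision will look less favourable than a bare percentage does.
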